## RESPONSE CRITERIA

**Complete Response (CR):** Disappearance of all target lesions. Any pathological lymph nodes (whether target or non-target) must have reduction in short axis to  $< 10$  mm.

**Partial Response (PR):** At least a 30% decrease in the sum of the diameters of target lesions, taking as reference the baseline sum diameters.

**Progressive Disease (PD):** At least a 20% increase in the sum of the diameters of target lesions, taking as reference the smallest sum on study (this includes the baseline sum if that is the smallest on study). In addition to the relative increase of 20%, the sum must also demonstrate an absolute increase of at least 5 mm. (Note: the appearance of one or more new lesions is also considered progression.)

**Stable Disease (SD):** Neither sufficient shrinkage to qualify for PR nor sufficient increase to qualify for PD, taking as reference the smallest sum diameters while on study.

---

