## MEASUREMENT OF EFFECT - CHEMOTHERAPY

**Timing of response assessment:** In addition to a baseline scan (obtained within 35 days prior to registration), patients' response to chemotherapy will be evaluated immediately upon surgical tumor resection per routine care guidelines and according to institutional practice.

**Methods of response assessment:** Response and progression will be evaluated in this study using the new international criteria proposed by the revised RECIST guideline (version 1.1). Changes in the largest diameter (unidimensional measurement) of the tumor lesions are used in the RECIST criteria.

**Evaluable for objective response:** Only those patients who have measurable disease present at baseline, have received at least one cycle of neoadjuvant chemotherapy, and have had their disease re-evaluated upon surgical tumor resection will be considered evaluable for response. These patients will have their response classified

according to the definitions stated below. (Note: Patients who exhibit objective disease progression prior to the end of cycle 1 will also be considered evaluable.)

**Evaluable Non-Target Disease Response:** Patients who have lesions present at baseline that are evaluable but do not meet the definitions of measurable disease, have received at least one cycle of therapy, and have had their disease re-evaluated will be considered evaluable for non-target disease. The response assessment is based on the presence, absence, or unequivocal progression of the lesions.

**Measurable disease:** Measurable lesions are defined as bladder lesions that can be accurately measured in at least one dimension (longest diameter to be recorded) as  $\geq 2$  cm by cystoscopy or CT scan, MRI, or calipers by clinical exam. All tumor measurements must be recorded in millimeters (or decimal fractions of centimeters).

**Non-measurable disease:** All other lesions (or sites of disease), including small lesions (longest diameter  $< 2$  cm), are considered non-measurable disease for purposes of this study.

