**Target lesions:** Any measurable bladder lesions up to a maximum of 2 lesions per bladder and 4 lesions in total, should be identified as target lesions and recorded and measured at baseline. Target lesions should be selected on the basis of their size (lesions with the longest diameter), be representative of all lesions, but in addition should be those that lend themselves to reproducible repeated measurements. It may be the case that, on occasion, the largest lesion does not lend itself to reproducible measurement in which circumstance the next largest lesion which can be measured reproducibly should be selected. A sum of the diameters (longest for non-nodal lesions, short axis for nodal lesions) for all target lesions will be calculated and reported as the baseline sum diameters. The baseline sum diameters will be used as reference to further characterize any objective tumor regression in the measurable dimension of the disease.

**Non-target lesions:** All other lesions (or sites of disease) including any measurable lesions over and above the target lesions should be identified as non-target lesions and should also be recorded at baseline. Measurements of these lesions are not required, but the presence, absence, or in rare cases unequivocal progression of each should be noted throughout follow-up.

**Methods for Evaluation of Measurable Disease:** All measurements should be taken and recorded in metric notation using a ruler or calipers. All baseline evaluations should be performed as closely as possible to the beginning of treatment and never more than 4 weeks before the beginning of the treatment.

---

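### Complete response is allowed with a persisting non-nodal non-target lesion, progression of an existing non-target lesion is never progressive disease, and patients with only non-measurable lesions have no category

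*Protocol*

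**What the plan says.** All references are to the protocol.

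- **MEASUREMENT OF EFFECT - CHEMOTHERAPY, lesion definitions.** Only bladder lesions of at least 2 cm are measurable. At most 2 per bladder, and 4 in total, become targets. Everything else is non-target, including measurable lesions beyond that limit. For these, "Measurements of these lesions are not required, but the presence, absence, or in rare cases unequivocal progression of each should be noted throughout follow-up".
- **Same section, evaluability.** Objective response is confined to patients with measurable disease at baseline, and those patients are sent to the definitions that follow. Patients with only non-measurable lesions have their own heading, where "The response assessment is based on the presence, absence, or unequivocal progression of the lesions". No categories are given there.
- **RESPONSE CRITERIA.**
  - CR: "Disappearance of all target lesions", and "Any pathological lymph nodes (whether target or non-target) must have reduction in short axis to" less than 10 mm.
  - PR: "At least a 30% decrease in the sum of the diameters of target lesions, taking as reference the baseline sum diameters".
  - PD: "At least a 20% increase in the sum of the diameters of target lesions, taking as reference the smallest sum on study", with an absolute increase of at least 5 mm. A new lesion also counts as PD.
  - The remaining category, stable disease (SD), is defined from the target sum alone, as "Neither sufficient shrinkage to qualify for PR nor sufficient increase to qualify for PD, taking as reference the smallest sum diameters while on study".
- **STATISTICAL CONSIDERATIONS, evaluation for response.** A specimen, one cycle of chemotherapy and re-evaluation at surgery are enough to be evaluable. Measurable disease is not mentioned.

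**The concern.** The section on measuring effect asks for an assessment that the category rules then leave out. The rules touch non-target disease in only two places: lymph nodes in the CR rule and new lesions in the PD rule. They are silent on an existing non-nodal non-target lesion that persists, and on any existing non-target lesion that progresses.

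This matters because the category is the reference against which motility contrast tomography (MCT) is judged. SPECIFIC AIMS and STATISTICAL CONSIDERATIONS both say response is measured by RECIST v1.1, and the primary question is how well the MCT prediction correlates with confirmed response. Where the omission changes a label, it makes the outcome more favourable than the lesions recorded. DATA AND RECORD KEEPING lists objective response and, if available, CT scans, but no lesion-level non-target status, so a label may be hard to correct later.

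**Working it through.** No stated figure is in dispute, so the check applies the RESPONSE CRITERIA literally and then with the change proposed below.

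**Setting.** Baseline target sum 30 mm (an arbitrary example), no new lesions, any pathological nodes below 10 mm.

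**Percentage changes.**
- 30 to 0 mm: (30 − 0)/30 = 100% decrease
- 30 to 18 mm: (30 − 18)/30 = 40% decrease
- 30 to 27 mm: (30 − 27)/30 = 10% decrease
- 30 to 39 mm: (39 − 30)/30 = 30% increase, 9 mm absolute, above the 5 mm minimum

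| Target lesions | As written, whatever the non-target status | Changed rule: non-target absent | Changed rule: non-target present | Changed rule: non-target unequivocally progressing |
|---|---|---|---|---|
| Gone | CR | CR | PR | PD |
| −40% | PR | PR | PR | PD |
| −10% | SD | SD | SD | PD |
| +30% | PD | PD | PD | PD |
| No target lesion | none assignable | to be decided | to be decided | to be decided |

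**Reading the table.**
1. As written, the category never changes with non-target status in any of the 5 × 3 = 15 combinations.
2. With a target lesion there are 4 × 3 = 12 combinations. The change alters 4: targets gone with a non-target present (CR to PR), and non-target progression with targets gone (CR to PD), −40% (PR to PD) or −10% (SD to PD). In the first of these the patient becomes PR because a 100% decrease also meets the 30% rule.
3. If response means CR or PR, responder status changes in 2 of the 4: non-target progression with targets gone or at −40%. If response means CR alone, it also changes in 2: targets gone with a non-target present, and targets gone with non-target progression. The protocol does not say which cut applies.
4. With no target lesion there is no sum of diameters, so PR, SD and sum-based PD cannot be evaluated. Only a new lesion gives a clear result (PD).

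These are combinations, not patients.

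**Numbers of patients.** STATISTICAL CONSIDERATIONS gives 500 enrolled and 20-30% evaluable: 500 × 0.20 = 100 and 500 × 0.30 = 150. The share with non-target lesions, and the share of those discordant with the targets, are not stated. Purely as an assumption, 20-40% and 5-15% would give 100 × 0.20 × 0.05 = 1 to 150 × 0.40 × 0.15 = 9 patients with a changed category. Not all of these would change responder status. Neither rate has support in the document.

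**The case against.** **RECIST v1.1 is adopted by reference, so the criteria could be an abbreviated summary of target response.** This is a fair reading of intent. But the protocol sends patients to its own written definitions, and where those assign CR or PR a site sees no gap to fill. At best there are two possible answers.

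**The primary endpoint is pathological response at surgery.** That is so in SPECIFIC AIMS, but the same section, STATISTICAL CONSIDERATIONS and the outcome-data step of Appendix B all tie response to RECIST v1.1. The gap therefore still reaches the reference outcome.

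**Few patients would change responder status.** Much of this stands. Moving from CR to PR leaves a patient a responder if response is CR or PR, and SD to PD is non-response either way. The protocol describes unequivocal progression of non-target lesions as rare and asks that targets be representative of all lesions.

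**Stronger readings that the document does not support.**
- A reader might infer that non-target disease is ignored altogether. It is not: CR covers non-target nodes and PD covers new lesions.
- A reader might infer that a patient with no target lesion meets CR automatically, there being nothing left to disappear. The measurement section confines objective response to patients with measurable disease and points only those patients to the definitions. What remains is the conflict with the statistical section, which drops that condition, and the lack of any category for these patients.

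**Conclusion.** The point holds in a limited form. The written CR rule disregards persistence of existing non-nodal non-target lesions (under 2 cm, or beyond the target limit), and the PD rule disregards unequivocal progression of any existing non-target lesion, although the protocol requires both to be recorded. The error that clearly crosses responder status is CR or PR on targets with non-target progression. Persistence crosses it only if response is CR alone.

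Patients with only non-measurable lesions are a separate inconsistency: outside objective response in the measurement section, evaluable in the statistical section, and without a defined outcome in either.

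No count of affected patients, and no estimate of the bias in the MCT correlation, follows from the document. The conclusion rests on applying the category rules as written. It does not depend on the assumed rates above. It should be corrected before outcomes are classified.

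**What to change.** 1. In RESPONSE CRITERIA, add to CR that all non-target lesions must also have disappeared, keeping the existing node condition.
2. Add to PD that unequivocal progression of an existing non-target lesion counts. State that PD takes precedence over CR, PR and SD, since shrinking targets with progressing non-target disease would otherwise meet two definitions.
3. Reconcile the evaluability text in MEASUREMENT OF EFFECT - CHEMOTHERAPY with that in STATISTICAL CONSIDERATIONS. State whether patients with non-target disease only enter the primary analysis and, if so, which outcome categories apply. Either choice is workable; the document does not settle it, and counting them as non-responders by default would not be justified.
4. State whether response means CR alone or CR plus PR.
5. Add non-target status to the data collection form.

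The cost is a few sentences and one form field, using assessments already required. The downside is slightly fewer CRs and responders.

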## MEASUREMENT OF EFFECT – MOTILITY CONTRAST TOMOGRAPHY

The foundational data structure that is obtained by MCT is a time-frequency spectrogram. This spectrogram captures how the Doppler frequencies of intracellular motion respond to the applied drug. This data structure is two-dimensional and can exhibit a variety of patterns that have been associated with mechanistic response of the tissue to the drug. To further improve the interpretation of the MCT results, numerous metrics have been developed that quantify the cellular response. These include: Backscatter brightness, NSD, change in NSD, dipole sine response, dipole cosine response, and quadrupole response. A further set of metrics, that are linearly dependent on the previous metrics, have more direct cellular mechanistic basis. These include: mitotic index, apoptotic index, necrotic index, metabolic activity, and membrane ruffling. These metrics are non-orthogonal, and a patient will often show strongly correlated responses among these metrics. Multiparameter logistic regression is performed on these metrics to provide a single-valued predictor of therapy response.

---

## DRUG FORMULATION AND PROCUREMENT

NOTE: All therapy in this trial is standard of care. All drugs to be tested in this study are commercially available formulations procured, stored, and administered in accordance with routine care standards and institutional policy. The primary therapies that will be screened using MCT in this study will include the following list, but may be supplemented from time to time at the investigators discretion. Therapies are listed in order of descending priority, with lower priority therapies tested subject to availability of sufficient tissue quantity. When tissue quantity permits, both combination and monotherapies will be imaged using MCT.

- DDMVAC (dose-dense methotrexate, vinblastine, doxorubicin, and cisplatin)
  - Gemcitabine and cisplatin
  - CMV (cisplatin, methotrexate, and vinblastine)

**STUDY COSTS:** All non-routine care procedures including the preparation, handling, and transport of MCT specimens, MCT assay procedures, and reporting of outcome data will be paid for by the study.

**SAFETY CONSIDERATIONS:** NOTE: All procedures and therapy in this trial are standard of care. Since the study does not entail any intervention in patients' care, only adverse events related to the loss of patient confidentiality will be reported to the IRB at the time of continuing review.

## STATISTICAL CONSIDERATIONS

**STUDY DESIGN:** This is a non-randomized, multi-arm, multi-center, feasibility study, designed to examine the feasibility of using MCT as a chemosensitivity assay among bladder cancer patients by comparing ex-vivo MCT patterns consistent with chemotherapy response and resistance to confirmed pathological response or resistance as measured by Response Evaluation Criteria in Solid Tumors (RECIST) v1.1 criteria.

**DEFINITION OF PRIMARY OUTCOME ENDPOINT:** Feasibility is defined as a high statistical correlation between MCT-predicted response, and surgically confirmed response to neoadjuvant chemotherapy.

**ANALYSIS PLAN FOR PRIMARY OBJECTIVE:** The study will be considered successful, if a majority of specimens yield interpretable MCT results, and if MCT signatures are identified which demonstrate a high statistical correlation to confirmed patient response.

**EXPLORATORY ANALYSIS:** Due to the inadequate samples size, no formal analysis is planned. Descriptive analysis of the correlation between MCT parameters and clinical outcome measures will be performed.

**DETERMINATION OF SAMPLE SIZE:** A target sample size of 500 patients was selected for initial enrollment using the investigators' previous research experience to approximate the appropriate number needed to demonstrate the feasibility of this technique. It is anticipated that only 20-30% of enrolled patients will yield specimens evaluable for response. It is estimated that it will take approximately 6-12 months to complete accrual.

**EVALUATION FOR RESPONSE:** Participants who provide a bladder tumor specimen, have received at least one cycle of chemotherapy, and have had their disease re-evaluated upon surgical resection will be considered evaluable for response.

**REPLACEMENTS:** Participants who withdraw from the study prior to having the TURBT procedure or fail to complete at least one evaluation for response will be replaced. No reported data will be included for participants who are replaced.

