## SPECIFIC AIMS

The primary study objective is to examine the feasibility of using MCT as a chemosensitivity assay among bladder cancer patients receiving neoadjuvant chemotherapy by comparing MCT patterns consistent with chemotherapy response or resistance ex-vivo to confirmed response or resistance to chemotherapy as measured by Response Evaluation Criteria in Solid Tumors (RECIST) v1.1 criteria.

**PRIMARY ENDPOINT:** Objective pathological response measured at the time of surgery.

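### The success rule asks for a high correlation without naming a measure or a value, and does not require it to hold outside the patients in whom the signature was found

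*Protocol*

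**What the plan says.** Under Statistical Considerations, the analysis plan for the primary objective has two limbs. The first asks that more than half of the specimens be interpretable. The second is met "if MCT signatures are identified which demonstrate a high statistical correlation to confirmed patient response". The endpoint definition uses the same term: "Feasibility is defined as a high statistical correlation between MCT-predicted response, and surgically confirmed response to neoadjuvant chemotherapy". Neither place names a coefficient, a minimum value or a confidence limit.

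The section on measurement of effect by MCT lists six metrics and five more that depend linearly on them, and adds: "Multiparameter logistic regression is performed on these metrics to provide a single-valued predictor of therapy response". No coefficients, cut-off or training set are given, and no hold-out set or cross-validation is mentioned.

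On numbers, 500 patients are to be enrolled and "It is anticipated that only 20-30% of enrolled patients will yield specimens evaluable for response". Participants who withdraw before the TURBT or "fail to complete at least one evaluation for response will be replaced". On drugs, three regimens are listed in order of priority, and "When tissue quantity permits, both combination and monotherapies will be imaged using MCT".

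**The concern.** Finding a signature is a fair aim for a feasibility study. The difficulty is that finding one is also the pass criterion. Without a measure and a value, the same result can be called success or failure once it has been seen. Without a requirement outside the fitting patients, the figure judged can be the one computed in the data that produced the model, which is biased upwards. The Project Summary makes a high predictive value the basis for larger trials and for rapid commercialization, so the verdict on this rule has consequences.

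**Working it through.** **Inputs**
- Enrolment 500, evaluable fraction 20-30% (Determination of Sample Size): 500 × 0.20 = 100; 500 × 0.30 = 150.
- Being evaluable for response does not require an interpretable MCT result, and the first limb needs only a majority. The analysed n could therefore approach 0.5 × 100 = 50 to 0.5 × 150 = 75. If every non-evaluable patient were replaced, it would move towards 500.
- Metrics: six, since the other five are linear in them.
- Responders: 20-60%. This is an assumption, taken from the Project Summary's range for chemotherapy in general.
- Correlation: fitted probability against observed response. This is also an assumption, since the protocol names no coefficient.

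The protocol prints no target correlation, alpha or power, so apart from the 100-150 there is no figure of its own to reproduce.

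**Hand check, uninformative metrics.** For a linear fit of k noise predictors, the mean of R² is k/(n − 1), so the apparent correlation is near √(k/(n − 1)):
- n=50: √(6/49) = 0.35
- n=100: √(6/99) = 0.25
- n=150: √(6/149) = 0.20
- n=500: √(6/499) = 0.11

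The chance of reaching r is the upper tail, on k and n − k − 1 degrees of freedom, of F = (r²/k) / ((1 − r²)/(n − k − 1)):
- n=100, r=0.3: F = (0.09/6)/(0.91/93) = 1.53, tail 18%
- n=150, r=0.3: F = (0.09/6)/(0.91/143) = 2.36, tail 3%
- n=50, r=0.4: F = (0.16/6)/(0.84/43) = 1.37, tail 25%

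**Simulation, uninformative metrics.** One logistic model, fitted and scored in the same patients:

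| | n=100 | n=150 |
|---|---|---|
| Mean apparent correlation (true 0) | about 0.24 | about 0.19 |
| Mean apparent AUC (true 0.50) | 0.64-0.67 | 0.61-0.64 |
| Reaches r = 0.3 | 17-24% | 3-6% |
| Reaches r = 0.4 | 1-4% | at most 0.2% |
| Reaches r = 0.5 | at most 0.3% | almost never |

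At n=50 with 20-40% responders, 0.4 is reached in about 26-33% of runs. At n=500 the mean apparent correlation is about 0.11. The simulation agrees with the hand check.

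**Simulation, weak assay.** Attainable AUC 0.65 (the AUC if the best coefficients were known), 40% responders. The ranges in the last two rows span separate runs:

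| | n=100 | n=150 |
|---|---|---|
| Mean apparent AUC | 0.70 | about 0.68 |
| Mean AUC in new patients | 0.61 | 0.62 |
| Apparent AUC reaches 0.70 | 47-50% | 32-36% |
| Cross-validated AUC reaches 0.70 | 7-8% | 3-7% |

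**The case against.** **A statistical analysis plan may settle this.** The choice of coefficient and the validation scheme are often left to such a plan. But the protocol itself prints the pass rule and leaves its deciding word open, so a rule stated here is badly fixed.

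**A predictor may already exist.** The endpoint definition speaks of a response that MCT has predicted, and Specific Aims of "MCT patterns consistent with chemotherapy response or resistance ex-vivo". The Project Summary cites earlier animal, xenograft and human studies. Being the first human trial in bladder cancer does not exclude a rule trained elsewhere. This stands in part. A reader might infer that the protocol plans to fit and score the predictor in the same patients, but it does not say so. It only permits it: signatures are to be identified, and no rule is given. If a locked rule exists, the apparent-fit figures do not apply, but the missing value remains.

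**The aim is modest.** The protocol calls this a feasibility study and states "Due to the inadequate samples size, no formal analysis is planned". A reader might take that sentence as withdrawing the success rule or contradicting it. It stands under the exploratory heading and does neither.

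**The harm depends on numbers the protocol does not print.** This is fair. The 17-24% matters only if 0.3 counts as high, and the weak-assay contrast uses an AUC of 0.70 that is not the protocol's. That the risk turns on an unprinted number is, however, the point.

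**Choice among drugs.** Picking the best of three regimens (between-regimen correlation 0.5) would raise the chance of reaching 0.3 to 40-50% at n=100. That assumes all three are imaged in every patient. Lower-priority regimens are tested only if tissue allows, and the regimen given is recorded, so matching is possible. The main finding does not rest on this.

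**Conclusion.** The point holds in this form: the second limb of the success rule has no measure, no value and no requirement beyond the patients in whom the signature was found, so it can be met on apparent fit. It should be fixed.

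The size depends on the missing number and on the analysed n. At n=100-150 a useless assay may reach 0.3 by chance but almost never 0.5, and a weak assay gains about 0.06-0.09 in AUC (0.68 − 0.62; 0.70 − 0.61).

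Two stronger readings are not supported. One is that a useless assay would probably pass: no value of *high* is printed, and at n=100-150 a demanding value would exclude it. The opposite reading, that a useless assay could hardly ever look strong, is not established either, because n could approach 50.

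The figures assume six independent normal metrics, one logistic model fitted in this cohort and 20-60% responders. The direction of the bias, if the model is fitted here, does not depend on the last of these.

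**What to change.** In Statistical Considerations, change both the success rule and the endpoint definition:
- Judge success on an internally validated figure, for example a cross-validated AUC or correlation, with metric and drug selection repeated inside each fold. Report it with its 95% confidence interval.
- Name the measure and print a minimum value, chosen by the sponsor before outcomes are linked to MCT results.
- Label apparent fit as descriptive.
- If a prediction rule already exists, print its coefficients and cut-off and judge that rule directly instead.

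A cross-validated AUC of at least 0.70 is one worked example and not a required value. Simulated pass rates at that value, with 20-60% responders at n=100 and n=150:

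| Assay | n=100 | n=150 |
|---|---|---|
| Uninformative | at most 1.1% | at most 0.4% |
| Attainable AUC 0.75 | 50-61% | 60-71% |
| Attainable AUC 0.80 | 77-90% | 87-96% |

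At n=50, attainable AUC 0.75 passes in only about 40%. A minimum of 0.65 would pass attainable AUC 0.75 in 72-85% / 83-93% (n=100 / n=150) and an uninformative assay in 1-4% / at most 1.7%.

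The change needs revised wording in two places and some analysis code, and no extra patients. The reported figure will be lower, and a working assay can fail, more often if few specimens are interpretable.
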